## 7.1 Humoral Immunogenicity

Immunogenicity testing will be performed on samples obtained from subjects of all three groups on trial Visit 1, Visit 3, Visit 4, FU1 and FU 2. Further, immunogenicity testing will be performed on samples obtained from subjects of Group 3 on trial Visits 6 and 7. Blood samples obtained on vaccination visits (i.e., Visit 1, Visit 3 and Visit 6) will be drawn prior to vaccination.

Antibody responses to MVA-BN® smallpox vaccine will be measured using a vaccinia-specific ELISA and vaccinia-specific PRNT, both assays established and validated at BN. The immunogenicity analysis will be performed at BN. All personnel involved in immunogenicity testing will be blinded to subject randomization details.

The procedures for the analytical tests performed are outlined in [Sections 7.1.1](#) and [7.1.2](#) below. The SOPs, effective at the time of testing will be filed in the electronic Trial Master File.

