#### Per Protocol Set (PPS):

This is the subset of subjects in the FAS who have received all vaccinations, completed all visits of the active trial phase (Visit 1 to Visit 5 and additionally Visit 6 to Visit 8 for Group 3) and

adhered to all protocol conditions. Subjects with only minor (not relevant) protocol deviations are included into this dataset.

The decision whether a protocol deviation is major or not for the classification of subjects into the various subsets will be made on a case-by-case basis in a data review meeting prior to database lock.

The main analysis of the immunogenicity endpoints will be performed on the PPS. The same statistical procedures will also be applied to the FAS.

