### FU Phase

All data collected after completion of Visit 5 (Groups 1 & 2) or Visit 8 (Group 3) until, and including, the 1 year Follow-up (FU 2) Visit. Note that for some subjects for whom the six months FU 1 Visit was not performed there may be FU 2 data available. Missing FU 1 or FU 2 Visit data will be considered a minor protocol violation (see [Table 1](#)).

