#### 3.2.2 Per Protocol Set (PPS)

This is the subset of subjects in the FAS who have received all vaccinations, completed all visits of the active trial phase (Visit 1 to Visit 5 and additionally Visit 6 to Visit 8 for Group 3; see [Table 1](#)) and adhered to all protocol conditions. Subjects with only minor (not relevant) protocol deviations are included into this dataset.

The decision whether a protocol deviation is major or not will be made on a case-by-case basis in a data review meeting (DRM) prior to database lock.

Examples of major protocol violations are:

1. Premature discontinuation of the trial before Visit 5 for Groups 1 and 2 or Visit 8 for Group 3 (the question “prematurely terminated the trial?” is answered with “yes” even where no other reason exists to exclude the subject from further participation in accordance with the protocol)
2. Subject did not meet all of the inclusion criteria
3. Subject met one or more of the exclusion criteria
4. Withdrawal from the second and/or third vaccination

- 
5. Major vaccine preparation and administration deviation from specification as given in the protocol including cases where the subject fulfils at least one of the criteria specified in the protocol for withdrawal from vaccination
  6. Major deviations of the visit window as determined during the DRM(s)
  7. Unallowed prior or concomitant medication
  8. Missing humoral immune response data (ELISA and PRNT) at Visit 1 or 4 (or Visit 7 for Group 3)

A classification of all subjects in the FAS for major protocol deviations will be performed at the time of the DRM.

The main analysis of the immunogenicity endpoints will be performed on the PPS. The same statistical procedures will also be applied to the FAS.

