### **3.4.3 Immunogenicity Variables**

Seropositivity (yes/no) at Visits 1, 3, 4, 6, 7 and FU 1 and FU 2

- Vaccinia-specific neutralizing antibodies (PRNT)
- Total vaccinia-specific antibodies (ELISA)

Seroconversion (yes/no) at Visits 3, 4, 6, 7 and FU 1 and FU 2

- Vaccinia-specific neutralizing antibodies (PRNT)
- Total vaccinia-specific antibodies (ELISA)

Antibody titers at Visits 1, 3, 4, 6, 7 and FU 1 and FU 2

- Vaccinia-specific neutralizing antibodies (PRNT)
- Total vaccinia-specific antibodies (ELISA)

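### The per-protocol set for immunogenicity depends on visits without an immunogenicity sample, and the SAP lists stopping after the last active-phase titre as a major violation (minor point)

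*SAP*

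**What the plan says.** Protocol 9.3 and SAP 3.2.2 use the same visit condition: a PPS subject must have "completed all visits of the active trial phase (Visit 1 to Visit 5 and additionally Visit 6 to Visit 8 for Group 3"). That means Visits 1 to 5 in every group and also Visits 6 to 8 in Group 3. The SAP adds: "The main analysis of the immunogenicity endpoints will be performed on the PPS". The same procedures are then applied to the FAS.

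Protocol 7.1 sets immunogenicity testing on "samples obtained from subjects of all three groups on trial Visit 1, Visit 3, Visit 4, FU1 and FU 2", and further on "samples obtained from subjects of Group 3 on trial Visits 6 and 7". SAP 3.4.3 matches this: "Antibody titers at Visits 1, 3, 4, 6, 7 and FU 1 and FU 2". The task lists for Visits 2, 5 and 8 in Protocol 4.2.2 contain no immunogenicity draw.

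Two further parts of SAP 3.2.2 matter:

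- **Minor deviations.** Subjects with only minor deviations stay in the PPS. The data review meeting decides major or minor case by case before database lock.
- **Examples of major violations.** Example 1 is premature discontinuation before Visit 5 (Groups 1 and 2) or Visit 8 (Group 3), and it applies even when nothing else would exclude the subject. Example 8 is missing antibody data at Visit 1 or 4, or at Visit 7 in Group 3. An isolated missed Visit 2, 5 or 8 is not among the eight examples.

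**The concern.** A per-protocol set for immunogenicity should keep subjects who received the assigned vaccinations and have valid titres. Attendance at Visits 2, 5 and 8 changes neither the doses given nor the titres already measured. Missing titres have their own criterion in example 8, and eligibility, vaccination, visit windows and medication are covered by examples 2 to 7.

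Two situations need to be kept apart.

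1. **Stopping after the last active-phase sample.** A Group 1 or 2 subject with both vaccinations and sera at Visits 1, 3 and 4 who stops before Visit 5 meets example 1. So does a Group 3 subject who stops between Visits 7 and 8. If example 1 is followed, a Visit 4 or Visit 7 titre needed for a secondary endpoint leaves the main analysis.
2. **Missing a single safety visit.** The definition asks for all visits, but the minor-deviation clause lets the subject stay. The outcome is discretionary. The trial is open-label, and although Protocol 7.1 blinds the laboratory staff, neither document says that the data review meeting is blinded. The decision could be made with the group known.

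Group 3 has three such visits and Groups 1 and 2 have two, so a literal reading falls slightly harder on Group 3 in its comparisons with the other groups.

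**Working it through.** **Visit check**

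| Visit | Required for PPS | Immunogenicity serum |
|---|---|---|
| 1, 3, 4 | all groups | yes |
| 2, 5 | all groups | no |
| 6, 7 | Group 3 | yes |
| 8 | Group 3 | no |

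**The plan's own figure.** SAP 3.1 gives 30 per group, a two-group t-test, 5% two-sided, a difference of 0.74 SD and 80% power. With noncentrality 0.74/√(1/30 + 1/30) = 2.87 on 58 degrees of freedom, power is 80.5%. The stated figure is reproduced. The difference detectable with 80% power is 0.736 SD.

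**Subjects lost.** The documents give no missed-visit or dropout rate. I assume a rate q per visit, independent between visits, with sera otherwise intact.

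- Stopping between Visits 4 and 5 only: 30 × q
- Also excluding a missed Visit 2: 30 × [1 − (1 − q)²]
- Group 3, losing subjects at each of Visits 2, 5 and 8: 30 × [1 − (1 − q)³]

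| q | Stop before Visit 5 only | Visits 2 and 5 | Visits 2, 5 and 8 (Group 3) |
|---|---|---|---|
| 1% | 0.3 | 0.6 | 0.9 |
| 3% | 0.9 | 1.8 | 2.6 |
| 5% | 1.5 | 2.9 | 4.3 |

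**Effect on power at 0.74 SD** (same t-test, whole subjects)

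| Sizes | Power | 80% detectable difference |
|---|---|---|
| 30 v 30 | 80.5% | 0.736 SD |
| 29 v 29 | 79.1% | 0.749 SD |
| 28 v 28 | 77.6% | 0.762 SD |

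For Group 2 against Groups 1 and 3 combined, the first-listed immunogenicity comparison, 30 v 60 gives 90.5% and 28 v 56 gives 88.5%.

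On the SAP's PRNT SD of 0.85, the detectable fold difference moves from 10^(0.85 × 0.736) = 4.2 at 30 v 30 to 10^(0.85 × 0.762) = 4.4 at 28 v 28.

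**The case against.** The case for leaving the text alone has real weight.

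- **Exclusion for an isolated missed visit is not automatic.** A reader might infer that anyone who misses Visit 2 or 5 loses their titres from the main analysis. The documents do not say so, because the data review meeting can class the miss as minor. This objection stands for missed visits. It does not answer example 1, which lists early stopping as major.
- **The FAS repeats everything.** SAP 3.5.8 and the table index give each immunogenicity analysis for both sets, so no titre disappears from the report. This stands, but the FAS is not the main set, and it admits subjects with a single injection.
- **The visits are not empty.** Visit 2 has the ECG and troponin test that can reveal a reason to withhold the next vaccination. Visits 5 and 8 hold the last scheduled medication record (Groups 1 and 2, and Group 3, respectively). This makes completion of the active phase a defensible idea of adherence. It is a weak reason to discard a Visit 4 or 7 titre obtained before the record stopped.
- **Follow-up visits.** The SAP says: "Missing FU 1 or FU 2 Visit data will be considered a minor protocol violation". A reader might infer an inconsistency, since those visits do carry endpoint sera. There is none, because the PPS is defined on the active phase and follow-up lies outside it.
- **Bias.** A reader might infer that the rule selects on tolerability. That is possible, but nothing in the documents shows it.

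**Conclusion.** The point holds, at minor severity. The SAP's own example removes from the main immunogenicity analysis fully vaccinated subjects whose active-phase titres are complete, and it leaves isolated misses of Visits 2, 5 or 8 to unblinded discretion.

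The explicit exclusion costs about 0.9 of 30 per group at an assumed 3%, or 1.4 percentage points of power (80.5% to 79.1%). Adding missed Visit 2 at 3% brings the loss to about 1.8 of 30 and power to 77.6%. The interval at risk in Groups 1 and 2 is short: Visit 4 is 12 to 16 days and Visit 5 is 28 to 35 days after Visit 3, so they are 12 to 23 days apart.

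The endpoints affected are secondary and are presented as estimates with confidence intervals, so power here is a measure of precision. The primary safety endpoint is not affected. The sizes rest on assumed, independent rates and intact sera.

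**What to change.** In SAP 3.2.2, state that for the immunogenicity PPS the following are minor deviations, provided that all assigned vaccinations were given and the example 8 titres are present:

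- a missed Visit 2, 5 or 8;
- discontinuation after the last active-phase immunogenicity sample (Visit 4 in Groups 1 and 2, Visit 7 in Group 3).

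Reword example 1 to match. Record this in SAP 3.6, which currently lists no alterations from the protocol. Leave the visit-window rule (example 6) and the other criteria as they are; a new within-window condition would be stricter than example 6 and could drop more subjects.

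The cost is SAP wording before database lock, with no new data and no extra subjects. The downside is that the PPS would include a few subjects who did not complete safety follow-up and whose late medication record may be incomplete.

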### 3.3 Definitions, Data Conventions and Handling of Missing Data

#### 3.3.1 Missing Data

No imputation of missing titers will be performed.

For the analysis of safety data incomplete AE and medication start and end dates will be imputed in order to assign these events to the correct vaccination period.

Missing Vital Signs data for Visit 1 will be imputed using screening (or latest re-screening) values. However, this will be displayed as 'Baseline' values in the tables and listing for Vital Signs data without reference to whether the data originated from Visit 1 or SCR.

For prior and concomitant medication and AEs imputation of partial start and end dates will be done for analysis purpose according to the following rules:

Missing	Rule for start date	Rule for end date	Flag for imputation
Day	First of month*	Last of month*	D
Month †	1. January*	31. December*	M
Year †	no imputation	Last visit date	Y

\* Unless the imputed start date is before first visit date, in which case first visit date is used; or the imputed end date is after last visit date in which case last visit date available is used.

† It is assumed that a missing month implies a missing day as well, and that a missing year implies a missing month and day.

All data will be listed and summarized as captured in the eCRF. All listings will display the original dates as captured in the eCRF.

If the imputation of a partial start date of an AE leads to a start date prior to the date of first vaccination, it will be set to the date of first vaccination following the worst case principle.

### 3.3.2 Assignment of AEs to Vaccination Period

Each AE will be assigned to a vaccination period using date/time of vaccination and date/time of the start of the AE.

If start time is missing and start date of AE coincides with the date of a vaccination, the AE will be assigned to the vaccination period corresponding to the vaccination on this date.

Each AE starting at or after any vaccination not matching the definition of a solicited AE is defined as an unsolicited AE. If a solicited AE begins outside of the 8-day window following the previous vaccination it will be considered an unsolicited AE regardless of the preferred term. If start time is missing and start date coincides with date of any vaccination, it will be regarded as a treatment emergent adverse event (TEAE). If the start date is (partially) missing the AE will be regarded as a TEAE following the worst case principle.

If the AE cannot be assigned to a vaccination period because of a (partially) missing start date then it will be assigned to the overall vaccination period. Hence it is possible for the overall vaccination period to include more events than the sum of the individual vaccination periods.

AEs with onset after the active trial phase will be considered to fall within the FU phase. AEs with onset after the active trial phase but at or before the FU 1 visit will belong to FU 1 period. AEs with onset date after FU 1 but before FU 2 visit will belong to the FU 2 period.

### 3.3.3 General Considerations for AEs

MedDRA version 17.1 will be used for coding of AEs.

Duration of an AE is calculated as follows:

Unsolicited AE: expressed in [days]

- End date of AE – start date of AE + 1
- In case of (partially) missing start date or (partially) missing end date imputed dates will be used in the calculation.
- In case the AE is ongoing at the end date of the AE, the duration will not be calculated

Solicited AEs: expressed in [days]

end date of AE – start date of AE + 1

where

end date is the last day the symptom is defined as an AE

start date is the first day symptom is defined as an AE

(no matter if the AE occurred at every day between first day and last day).

- In case the AE is ongoing at the end date of the AE, the duration will not be calculated

Time interval between vaccination and start of AE are calculated as follows:

Relative day of start of AE is calculated as follows:

Unsolicited AEs: expressed in [days]

- Start date of AE – corresponding vaccination date
- In case of (partially) missing start date no calculation will be done.

Solicited AEs: expressed in [days]

- Start date of AE – corresponding vaccination date
- Where start date is the first day a symptom is defined as an AE, and vaccination day corresponds to Day 0.

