### 8.2.6 Solicited AEs

After each vaccination subjects receive a memory aid to record solicited local and general AEs most likely to occur on the day of vaccination and the following seven days (Days 0-7; 8-day period).

All solicited symptoms observed after vaccination with details concerning the intensity and the course of the reaction should be documented there. The investigator will collect this information during the following scheduled visits and transfer it to the eCRF and the subject's medical record. Local and general reactions still ongoing after seven days will be measured or examined each day until resolution or until no further change can reasonably be expected, and the last day of symptoms and maximum intensity will be documented in the memory aid.

In case of severe and unexpected local and/or general reactions, the subject should be instructed to contact the trial physician outside of scheduled trial visits.

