#### Safety and Reactogenicity

- Occurrence, relationship to the trial vaccine and intensity of any Adverse Event of Special Interest (AESI).
- Occurrence of any Grade 3 or 4 Adverse Events (AEs) probably, possibly or definitely related to the trial vaccine within 28 days after each vaccination.
- Occurrence, relationship to the trial vaccine and intensity of unsolicited non-serious AEs within 28 days after each vaccination.

- Occurrence, intensity and duration of solicited local AEs (redness, swelling, induration, pruritus and pain) during the 8-day period (day of vaccination and the following seven days) after each vaccination.
- Occurrence, relationship to the trial vaccine, intensity and duration of solicited general AEs (pyrexia, headache, myalgia, nausea, fatigue and chills) during the 8-day period (day of vaccination and the following seven days) after each vaccination.
- Change in CD4 T cell counts in Human Immunodeficiency Virus (HIV)-infected subjects two weeks after each vaccination.

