#### Solicited Local AEs

Solicited local AEs will be summarized by PT after each vaccination visit, and broken down by maximum intensity.

In addition, the incidence will be calculated by severity (i.e. the number of subjects developing a particular local solicited AE during the 8-day period after each vaccination divided by the number of subjects actually receiving this vaccination) with corresponding 95% Clopper-Pearson CI. The incidence will also be calculated for any solicited local AE for each vaccination period and per subject.

The duration of the AEs will be included in the listing. The duration of the AEs will also be summarized using the mean, SD, median, minimum and maximum.

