#### Solicited General AEs

Solicited general AEs will be summarized in the same manner as solicited local AEs.

In addition a similar summary table will be produced for relationship of the AEs to trial vaccine. Also the incidences of AEs with reasonable possibility of vaccine contribution (i.e. relationship to vaccine documented as “possible”, “probable”, “definite” or missing), and those with Grade  $\geq 3$  and with reasonable possibility of vaccine contribution will be summarized per vaccination period and overall by subject.

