#### 15.3.1.2 Solicited Local Adverse Events

- 15.3.1.2.1 Solicited Local Adverse Events (Per Vaccination Period): Summary of Maximum Intensity – FAS
- 15.3.1.2.2 Solicited Local Adverse Events (Per Subject): Summary of Maximum Intensity – FAS
- 15.3.1.2.3 Solicited Local Adverse Events (Per Vaccination Period): Incidence by Maximum

- Intensity – FAS
- 15.3.1.2.4 Solicited Local Adverse Events (Per Subject): Incidence by Maximum Intensity – FAS
- 15.3.1.2.5 Solicited Local Adverse Events (Per Vaccination Period): Summary of Duration – FAS
- 15.3.1.2.6 Solicited Local Adverse Events (Per Subject): Summary of Duration – FAS
- 15.3.1.3 Solicited General Adverse Events**
- 15.3.1.3.1 Solicited General Adverse Events (Per Vaccination Period): Summary of Maximum Intensity – FAS
- 15.3.1.3.2 Solicited General Adverse Events (Per Subject ): Summary of Maximum Intensity – FAS
- 15.3.1.3.3 Solicited General Adverse Events (Per Vaccination Period): Incidence by Maximum Intensity – FAS
- 15.3.1.3.4 Solicited General Adverse Events (Per Subject): Incidence by Maximum Intensity – FAS
- 15.3.1.3.5 Solicited General Adverse Events (Per Vaccination Period): Summary of Duration – FAS
- 15.3.1.3.6 Solicited General Adverse Events (Per Subject): Summary of Duration – FAS
- 15.3.1.4 Unsolicited Adverse Events**
- 15.3.1.4.1 Treatment Emergent Unsolicited Adverse Events (Per Vaccination Period): Incidence by Preferred Term and System Organ Class – FAS
- 15.3.1.4.2 Treatment Emergent Unsolicited Adverse Events (Per Subject): Incidence by Preferred Term and System Organ Class – FAS
- 15.3.1.4.3 Treatment Emergent Unsolicited Adverse Drug Reactions (Per Vaccination Period): Incidence by Preferred Term and System Organ Class – FAS
- 15.3.1.4.4 Treatment Emergent Unsolicited Adverse Drug Reactions (Per Subject): Incidence by Preferred Term and System Organ Class – FAS
- 15.3.1.4.5 Treatment Emergent Unsolicited Adverse Events (Per Vaccination Period): Summary of Intensity and Relationship to Trial Vaccination – FAS
- 15.3.1.4.6 Treatment Emergent Unsolicited Adverse Events (Per Subject): Summary of Intensity and Relationship to Trial Vaccination – FAS
- 15.3.1.4.7 Unsolicited Adverse Events: Incidence of Related Adverse Events by Preferred Term and System Organ Class (Per Subject) by Gender – FAS
- 15.3.1.4.8 Unsolicited Adverse Events: Incidence of Related Adverse Events by Preferred Term and System Organ Class (Per Subject) by Ethnicity – FAS

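### SAP 3.3.3 gives no duration to a solicited AE recorded as ongoing, sets no date for that judgement and plans no count, so episodes without a recorded resolution drop out of the duration summaries

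*SAP*

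**What the plan says.** The secondary safety endpoints in SAP 1.4.2 include "Occurrence, intensity and duration of solicited local AEs", and the same for solicited general AEs. SAP 3.3.3 computes the duration of a solicited AE as end date minus start date plus one, where "end date is the last day the symptom is defined as an AE". It then adds, for solicited and separately for unsolicited AEs: "In case the AE is ongoing at the end date of the AE, the duration will not be calculated".

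SAP 3.5.9 describes the summary for local reactions: "The duration of the AEs will also be summarized using the mean, SD, median, minimum and maximum". For general reactions, "Solicited general AEs will be summarized in the same manner as solicited local AEs". The table index has matching outputs per vaccination period and per subject, such as "Solicited Local Adverse Events (Per Vaccination Period): Summary of Duration". It has no duration table for unsolicited AEs, so in practice the rule matters for solicited AEs.

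On data collection, Protocol 4.2.2 has symptoms still present at Day 7 recorded daily until they resolve. Protocol 8.2.6 has them followed "until resolution or until no further change can reasonably be expected", with the last symptom day entered in the memory aid. The memory aid is collected at Visits 2, 4 and 7, each 12 to 16 days after a vaccination.

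**The concern.** An episode receives no duration precisely because it had not ended when last recorded. That makes the exclusion depend on the quantity being summarised. Even when a subject leaves for reasons unrelated to the reaction, a longer episode is more likely than a short one to be open on the day contact ends. The completed durations therefore tend to be too short as a sample of all durations.

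The wording adds a second difficulty. An AE that has an end date is not ongoing at that date, so the rule does not identify its own cut-off. Two programmers could apply it at memory-aid collection, at the last active visit or at FU 2, and obtain different tables.

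At stake is a descriptive safety output: how long local and general reactions last under each regimen, with 30 subjects per group. With so few subjects, one or two missing durations can change a group's maximum and visibly move its mean, and no planned table says how many are missing.

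**Working it through.** The documents state no duration, no share of ongoing episodes and no bias, so there is no plan figure to reproduce.

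**1. Which episodes the rule reaches**
- Resolved after Day 7: recording continues (Protocol 4.2.2 and 8.2.6) and the SAP end date has no Day 7 cap. The 8-day window governs onset (SAP 3.3.2). The episode gets a duration and is kept.
- Still present when the memory aid is collected: Protocol 4.2.3 has AEs ongoing at the last trial visit checked again at FU 1 and FU 2, and Protocol 8.2.5, headed for unsolicited AEs, sets the same follow-up. An episode whose resolution is recorded there can be kept. Neither document says how a solicited end date is updated after the memory aid has been handed in.
- Recording stopped because no further change was expected: a last symptom day is to be documented, but the SAP does not say whether this counts as an end date or as ongoing.
- Lost to follow-up, discontinued, or unresolved at last contact: no resolution on record, so no duration.

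**2. Contrast within the SAP**
Under SAP 3.3.1, an AE end date with the year missing is set to the last visit date. SAP 3.3.3 lets imputed dates enter the duration of unsolicited AEs. An unsolicited event whose end is unknown can thus get a long duration, while one known to persist gets none.

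**3. Direction and scale, by hand (all values assumed)**
Take 20 episodes in a group. Resolved ones average 3 days; each unresolved one was last seen at 15 days.
- One unresolved: the true mean is at least (19 × 3 + 1 × 15)/20 = 72/20 = 3.6 days; reported 3.0.
- Two unresolved: at least (18 × 3 + 2 × 15)/20 = 84/20 = 4.2 days; reported 3.0.

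**4. Dependence on when ongoing is judged (all values assumed)**
Simulation of 1,000,000 episodes per scenario: log-normal durations rounded up to whole days, median 2, 3 or 5 days, log-SD 0.6 or 0.9, onset on Day 0, 1 or 2 with probability 0.50, 0.35 and 0.15. Episodes still present after the cut-off are dropped. Understatement = (full mean − mean of the rest)/full mean. The range runs over the six scenarios.

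| Cut-off | Dropped | Smallest understatement | Largest understatement |
|---|---|---|---|
| Day 7 | 1.7% to 33.8% | 2.89 to 2.78 (4%) | 8.01 to 4.08 (49%) |
| Day 16 | 0.03% to 9.5% | 2.89 to 2.89 (0%) | 8.01 to 5.98 (25%) |
| Day 28 | 0% to 2.7% | 2.89 to 2.89 (0%) | 8.01 to 7.04 (12%) |
| Day 182 | about 0% | 2.89 to 2.89 (0%) | 8.01 to 8.00 (0.1%) |

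Day 7 is shown for scale only, since the protocol records beyond it. Day 16 is the latest memory-aid collection; Day 182 is the start of the FU 1 window. The median moved by at most one day at Day 16 and later.

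**5. Effect of using observed length**
With median 3 days and log-SD 0.9, the full mean is 4.99. At a Day 16 cut-off, dropping gives 4.38 (12% low); counting at observed length gives 4.73 (5% low). Part of the loss is recovered.

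**The case against.** A reader might infer that the rule strips the longest reactions from the summaries. The documents do not support that. A three-week induration that resolves, and whose last day is recorded, enters both the mean and the maximum. Nor are the missing durations necessarily the longest: a subject lost on Day 3 with a headache is missing whatever its eventual length. The tendency described above concerns averages and does not identify the top tail.

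A reader might also infer that the rule flatters the double-dose group. That would need more never-resolved reactions in Group 2, and nothing in the documents points to this. Protocol 2.6.2 reports no significant difference in the number or severity of events between a single high dose and the standard dose; it does not address duration.

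Further points on the other side are sound. Unresolved episodes stay in the incidence and intensity tables and in the listings. SAP 3.5.1 makes the number of observations standard for continuous summaries, so a shortfall against the number of events may be visible. The median is already planned and is barely affected. No test, sample size or decision rule uses duration.

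What remains is that the exclusion is a stated rule that depends on the outcome, its cut-off is undefined, and a shortfall in N would not tell the reader that the missing values are open episodes or how long they had lasted.

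**Conclusion.** The point holds as a minor, inexpensive improvement. Solicited AEs without a recorded resolution are left out of the duration summaries, no date defines that status, and no count is planned. The reported mean is understated when the dropped episodes are longer than the rest; the reported maximum can only be equal to or lower than the true one.

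The size cannot be determined from the documents. It is negligible if follow-up is complete. Under the assumed distributions it stays at or below 12% of the mean if episodes are followed to Day 28, and could reach 25% if ongoing were judged at Day 16. These figures rest on assumed log-normal durations and a single cut-off for everyone. They show how much turns on the undefined date; they do not predict this trial's results. The primary endpoint is untouched.

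**What to change.** In SAP 3.3.3, replace the rule for solicited AEs along these lines:
- An episode with no recorded resolution has its duration censored at the last day it was observed to be present, calculated as that day minus start date plus one.
- Define that day, for example as the latest date on which the memory aid or a later visit record shows the symptom. State how an episode is coded when recording stopped because no further change was expected.

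In the duration tables for solicited local and general AEs:
- Report the number and percentage of unresolved episodes by group and vaccination period.
- Show the maximum with observed lengths included, marked as ≥ x days where the longest is unresolved.
- Give the median with unresolved episodes treated as censored (Kaplan-Meier). This will usually differ little from the planned median; the count and the maximum are the more useful additions.

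The cost is a short SAP edit, slightly longer tables and a little more programming. No new data are needed.
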